# 1 Protocol Summary

Title:	Hospital-based Patient Navigation to Promote Smoking Cessation: a pilot RCT
Population:	Study population will include individuals (both men and women, all races and ethnicities) who meet inclusion criteria: (1) hospitalized smokers at BMC); (2) smoked at least 1 cigarette per day in the past month; (3) able to speak, read, and understand English; (4) able and willing to participate and provide informed consent; (5) has a primary care physician at Boston Medical Center; (6) at least 18 years of age; (7) must have plans to quit smoking; and (8) must have a working telephone.
	Sample size: 50
Intervention:	3 hours of patient navigation over the next 3 months
Objectives:	To assess effect of patient navigation to promote smoking cessation
Design/Methodology:	Enhanced Traditional Care : Participants randomized to this group will receive a resource card that has information on quitlines, BMC's outpatient program number, and websites for smoking cessation.
	Patient Navigation Intervention: We base our intervention on the
	Social Contextual Model, a multi-level approach to health education
	which stresses the influence of life experiences (e.g. stress and
	financial problems) and social relationships (e.g. social networks and family roles) on the practice of health behaviors.
	Intervention Components and Content. Participants will meet the
	navigator in person if she is available, or will be introduced by
	telephone. Participants will receive navigation from a trained
	navigator, based centrally in the Section of General Internal
	Medicine. Our navigator has a BA degree, and has extensive
	experience doing community health outreach. Participants will
	receive up to ten hours of patient navigation, in person or over the
	phone, over a 3-month period. We chose a ten-hour intervention dose based on 1) a prior study of motivational interviewing in low-income smokers and 2) our prior work studying patient navigation t promote smoking cessation. We have not designated a specific number of contacts, but allot a maximum of ten hours of patient
	navigation time per participant. The navigator will work flexible hours, contacting patients on evenings and weekends as necessary. Patient navigation contacts will involve individual counseling to help
	the patient achieve abstinence from smoking. Navigators will also screen participants for social determinants of health which may be preventing them from quitting smoking, using an adapted version o a validated social determinants of health screening tool. Patient navigation intervention calls will use motivational interviewing (MI)

strategies to do the following: (1) Assess stage of change for smoking

cessation; (2) Assess and reinforce any prior abstinence from smoking and/or any efforts made to reduce or quit smoking; (3) Explore the patient's motivation to quit smoking, drawing on recent

illness, financial situation, and family situation as appropriate; advise about the risks of smoking and benefits of quitting (4) Discuss past experience with utilizing cessation support; (5) Explore potential barriers to using smoking cessation medications (e.g. lack of trust, cost, misconceptions about treatment (e.g. that nicotine replacement therapy (NRT) is more harmful than cigarettes)); (6) Brainstorm strategies to address identified barriers; (7) Elicit commitment to accept another patient navigation counseling call, discuss timing.

Total Study Duration:	3 months
Subject Participation	3 months
Duration:	

# 2 Background/Rationale & Purpose

Smoking cessation interventions are the 'gold standard' of healthcare cost effectiveness because they achieve more lifeyears gained for fewer resources than other interventions. Although there are several effective, guideline-recommended cessation treatments, low-income and minority populations suffer a disproportionate burden of tobacco-related morbidity and mortality due to high smoking rates, lack of access to cessation services, and lack of support for quitting. Hospitalization presents an opportunity to reach smokers who otherwise may not seek tobacco treatment. It offers a 'teachable moment' during which the risks of smoking are highlighted, leaving smokers more receptive to cessation interventions. Highly intensive counseling interventions that begin during the hospital stay and continue with supportive contacts for at least one month after discharge increase smoking cessation rates post-hospitalization by 40%, among patients hospitalized at non safety-net hospitals. However, we are unaware of interventions for hospitalized smokers that are effective among minority and low SES smokers hospitalized at safety-net hospitals. In a recent RCT (in press at JAMA Internal Medicine), we demonstrated that patient navigation and financial incentives substantially increased biochemically confirmed smoking cessation at 12 months among minority and low-SES primary care smokers. Patient navigation is a low-cost approach in which a community member trained in motivational interviewing (MI) assesses barriers to accessing evidence-based tobacco treatment, and addresses underlying social determinants of health. While the intervention improved quit rates in the ambulatory setting, we have not tested the efficacy of the patient navigation intervention component among recently hospitalized smokers. By implementing the intervention among recently hospitalized smokers (who may be more motivated to quit smoking), we will increase the proportion of participants that receive the minimum intervention dose from the navigator. We propose to pilot-test patient navigation among recently hospitalized smokers in preparation for a larger randomized trial. We propose the following specific aims:

Aim 1. To adapt our previously developed patient navigation primary care-based smoking cessation intervention into a scalable intervention delivered to recently hospitalized smokers at a large urban safety-net hospital. We propose to add screening and referral for social determinants of health using a validated screening tool embedded into the navigator script. We will tailor the navigator role to the population of recently-hospitalized smokers, mapping to theoretical constructs of the Social Contextual Model.

Aim 2. To determine the acceptability and feasibility of the adapted patient navigation smoking cessation intervention by pilot-testing it among 25 smokers at a large urban safety-net hospital.

## 3 Objectives

#### 3.1 Study Outcome Measures

Primary Outcome: whether a prescription for an FDA-approved smoking cessation medication was sent to the participants' pharmacy (Y/N, based on chart review)

Secondary outcomes: Self-reported smoking cessation at 3 months, utilization of smoking cessation medication, stage of change assessed at baseline and 3 months, according to the following categories: pre-contemplation, contemplation, preparation, or action. For each participant, we compare stage of change at baseline vs. 3 months. We will also measure

level of nicotine dependence (baseline and 3 months), measured by the Fagerstrom Test for Nicotine Dependence, and use of other tobacco treatment support (3 months), defined as self-report of all tobacco treatment support received, including support from non-study sources, including the internet, during the 3-month study period.

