## 6 Study Subject Selection

## 6.1 Subject Inclusion Criteria

In order to be eligible to participate in this study, an individual must meet all of the following criteria:

- 1) Hospitalized smokers at BMC
- 2) At least 18 years of age
- 3) Must smoke at least one cigarette per day in the past month
- 4) Able to speak, read, and understand English
- 5) Able and willing to comply with all study protocols and procedures
- 6) Having a PCP in Boston Medical Center
- 7) Possession of a telephone (home or cell)
- 8) Must have plans to quit smoking

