#### 11.3 Statistical Methods

For categorical outcomes of engagement and self-report cessation, we plan to report percentages and 95% confidence intervals; for continuous outcomes we examine means, standard deviations, and ranges. In order to determine if the patient navigation condition achieves greater smoking cessation at 3-month follow-up compared to standardized inpatient counseling condition, we will compare groups using chi- square tests and note differences that are statistically significant at the  $\alpha$ < 0.05 level. Analyses will be based on intent-to-treat.

We will use multiple logistic regression to control for potential confounders identified in bivariate analyses as well as variables of *a priori* clinical significance (gender, age, race/ethnicity). We will evaluate odds ratios with 95% confidence intervals to determine the relative magnitude of the adjusted association for each variable. Independent variables with strong correlations may result in collinearity. To address collinearity, we will construct separate models, each with one of the variables, and assess both the C statistic and the coefficients for the other variables in the model. Dropouts and missing data: We expect the majority of missing data to be due to dropouts due to moving or failure to remain in the study. We will investigate whether missing data is associated with patient characteristics. While data may not be missing completely at random, it may be reasonable to assume that data are missing at random. If this is the case, multiple imputations methods originally developed for sample survey data is applicable to clinical trials with dropouts and shown to be effective. Analytic software: We will use SAS version 9.4 (SAS Institute Inc, Cary, NC).

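### Stage of change and nicotine dependence are measured at baseline and 3 months but get no between-arm comparison, and their baseline values go unused

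*Combined protocol and SAP*

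**What the plan says.** Section 3.1 lists stage of change as a secondary outcome, recorded in four ordered categories of which action is the highest. The only statement about its use is "For each participant, we compare stage of change at baseline vs. 3 months"; section 4 repeats it under the evaluation design. The same paragraph adds "level of nicotine dependence (baseline and 3 months), measured by the Fagerstrom Test for Nicotine Dependence", with no comparison attached.

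Section 11.3 names neither outcome. Its rules are:
- "For categorical outcomes of engagement and self-report cessation, we plan to report percentages and 95% confidence intervals". Stage is not among the outcomes named.
- "for continuous outcomes we examine means, standard deviations, and ranges". The dependence score falls here by type.
- A chi-square comparison of groups, introduced by "In order to determine if the patient navigation condition achieves greater smoking cessation at 3-month follow-up". This is the only between-arm test in the section.
- "We will use multiple logistic regression to control for potential confounders identified in bivariate analyses". The model's dependent variable is not named. Its pre-specified covariates are gender, age and race/ethnicity; neither baseline stage nor baseline dependence is listed.

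On entry, section 6.1 requires: "Must have plans to quit smoking". Section 4 is stricter and asks for a stated plan to stay quit after discharge. Section 8.1 is looser: its screening question accepts a quitting horizon written as six or more years. Section 4 also says that both arms receive inpatient cessation counselling, and that randomisation is stratified by the answer about quit plans.

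**The concern.** Randomisation makes the arms comparable, and a baseline measurement sharpens that comparison. For these two outcomes the plan uses neither.

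A before-after change mixes any effect of navigation with everything else that happens after a hospital stay: recovery from illness, the inpatient counselling given to both arms, and the fading of motivation that was high at enrolment. Only the control arm can separate these.

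Stage has a further problem. If people are admitted because they currently report readiness to quit, their readiness will tend to be lower on remeasurement even if nothing is done, and anyone already in the top category can only stay or fall. That would pull the within-person comparison downward in both arms and could hide a benefit.

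The pilot is meant to prepare a larger randomised trial. Without an arm difference and its interval, it passes on little about these two measures.

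**Working it through.** **The plan's own figures.** Fifty randomised 1:1 gives 50/2 = 25 per arm, which agrees with the 25 smokers in Aim 2. Section 4 expects at least 60% retention (stated for 1 month) and cites 70% at 3 months from prior work. So 0.60 × 50 = 30 and 0.70 × 50 = 35 completers, or 15 to 17.5 per arm. The documents give no SD, effect size, power or correlation. The correlations, truncation fractions and two-sided 5% level below are assumptions.

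**Is there a between-arm analysis elsewhere?** The chi-square test is for cessation. The logistic model suits a binary outcome, so as written it fits neither a four-category stage nor a continuous score. A baseline value could enter it only if bivariate screening happened to select it. No linear, ordinal or change-score comparison appears for either outcome.

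**Precision from using the baseline (continuous score).** With n per arm and r the baseline-to-3-month correlation in the enrolled sample:
- variance of the arm difference, 3-month score alone: 2·SD²/n
- variance adjusted for baseline: (1 − r²)·2·SD²/n
- equivalent gain in completers: 1/(1 − r²) − 1
- 95% CI half-width in SD units: 1.96·√[(1 − r²)·2/n]
- difference detectable with 80% power: (1.96 + 0.84)·√[(1 − r²)·2/n]

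| r | 1 − r² | gain | half-width, 15 / 17.5 per arm | detectable, 15 / 17.5 per arm |
|---|---|---|---|---|
| 0.3 | 0.91 | 10% | 0.68 / 0.63 | 0.98 / 0.90 |
| 0.5 | 0.75 | 33% | 0.62 / 0.57 | 0.89 / 0.82 |
| 0.7 | 0.51 | 96% | 0.51 / 0.47 | 0.73 / 0.68 |

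Unadjusted, the half-width is 0.72 / 0.66 SD.

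**Stage, if entry truncates readiness.** Suppose entry keeps the top 50% or top 70% of a normal readiness scale. The mean of those kept is m = 0.80 or 0.50 SD. With no effect of either arm, the expected within-person change is −(1 − r)·m, where r is now the unselected correlation:
- top 50%: −0.40 SD at r = 0.5, −0.24 SD at r = 0.7
- top 70%: −0.25 SD at r = 0.5, −0.15 SD at r = 0.7
- no selection on readiness: 0

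Truncation also lowers the correlation. The variance of the kept baseline is v = 0.363 (top 50%) or 0.493 (top 70%), and r′ = r√v / √(r²v + 1 − r²):
- lowest case, top 50% and r = 0.5: r′ = 0.301/0.917 = 0.33, gain 12%
- highest case, top 70% and r = 0.7: r′ = 0.491/0.867 = 0.57, gain 47%

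**What the drift does to a within-arm reading.** In 4,000 simulated trials per setting with no effect and r = 0.5, excluding the least ready 30% or 50%, a paired test within one arm rejected at the 5% level in 17% or 35% of trials at 15 per arm. The baseline-adjusted between-arm test stayed at about 5%. The plan names no paired test, so this illustrates the risk and does not describe the plan.

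**Proportion in action.** In the widest case (50% in each arm, 15 per arm), the 95% CI half-width is 1.96·√(2 × 0.25/15) = 0.36, or 36 percentage points.

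**The case against.** Both are secondary outcomes of a 50-person pilot whose aims are acceptability and feasibility, so descriptive reporting is defensible. The stage sentence sits among the outcome definitions and can be read as defining a per-person change variable. Section 11.3 names neither outcome, so the descriptive-only reading of dependence is inferred from a general rule. All this stands and limits the weight of the point. It does not supply a between-arm comparison.

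A reader might infer more than the documents support:
- *That within-person change will be presented as evidence for navigation.* The documents never say so.
- *That regression to the mean affects both outcomes.* Entry at one cigarette a day does not select high dependence, so the argument does not carry over to the Fagerstrom score.
- *That stage is certainly selected high and the drift would favour navigation.* Section 8.1's horizon excludes few people, and requiring current smoking may keep many out of the top category at baseline, so even the direction is not settled. A downward drift would mask benefit, not create it.
- *That imputation will give people who have stopped a smoker's score.* Imputation in 11.3 is conditional on a missing-at-random assumption and is aimed at dropouts and missing data. Someone interviewed at 3 months who has stopped is not a dropout. What stands is that no scoring rule is given.
- *That adjustment is worth 33 to 96% more completers for stage.* That range carries an unselected correlation into a selected sample.

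Two practical limits also stand. An ordinal model with baseline stage is fragile with 30 to 35 people. The proportion in action may overlap closely with self-reported cessation, which 11.3 already compares.

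**Conclusion.** The point holds as a modest, worthwhile improvement. As written, the plan makes no randomised comparison of stage of change or dependence and does not use either baseline value in one. This follows from the text and needs no assumption beyond reading 11.3's general rule as covering the Fagerstrom score.

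The sizes do rest on assumptions. For dependence, the gain is about 10% to 96% more effective completers as r goes from 0.3 to 0.7. For stage it is about 12% to 47% if entry truncates readiness as assumed. The possible null drift in stage is 0.15 to 0.40 SD downward under those assumptions and nil if entry does not select on readiness. A truncated normal is only a rough stand-in for four categories.

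No figure stated in the plan changes. Even after adjustment, only differences of about 0.7 to 1.0 SD would be detectable with 80% power, so the result is an estimate for planning and not a test of efficacy.

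**What to change.** Add to section 11.3, labelled exploratory:
- **Dependence:** a linear model of the 3-month Fagerstrom score on arm, baseline score and quit-plan stratum, reporting the adjusted arm difference with 95% CI.
- **Stage:** the proportion in action at 3 months by arm, with the difference and 95% CI; or, if the categories are not too sparse, an ordinal model on arm adjusted for baseline stage.
- **People who have stopped smoking:** state before the data are seen how their 3-month dependence score is handled, so that they are not dropped. Dropping them would select on the result the intervention aims for. Any summary restricted to continuing smokers is descriptive.
- **Within-person change:** keep as description, shown by arm, with the numbers analysed.

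Reconcile the quit-plan entry rules in sections 4, 6.1 and 8.1, since they determine how far baseline stage is selected and whether the stratum varies.

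The cost is wording in the plan and a small amount of analysis. The data are already being collected.

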# 4 Study Design

Study Site: We will recruit 50 hospitalized adults at Boston Medical Center (BMC).

Inclusion Criteria: age  $\geq$  18, English-speaking, Medicaid-insured, hospitalized on the general internal medicine or family medicine service and have a primary care provider at BMC; smoked  $\geq$ 1 cigarettes/day in the past month; when asked, "What is your plan about smoking after you leave the hospital?" response is either: "I plan to stay quit when I leave the hospital."

Exclusion Criteria: no telephone; expected hospital stay of <24 hours; cannot give informed consent or participate in counseling due to psychiatric or cognitive impairment or communication barrier; admitted to surgical, obstetric or psychiatric units; estimated life expectancy of <12 months; or medical instability.

Identification of potential participants: An EPIC programmer who works with the Inpatient Tobacco Treatment Program will identify potential participants using EHR data each week.

Recruitment, screening and consent procedures: Utilizing a daily roster of English-speaking hospitalized smokers, a trained research assistant will screen patients for study eligibility, obtain informed consent, conduct the baseline assessment, and randomly assign patients to study condition. Participants will receive a \$15 gift card for completing the baseline assessment. We estimate that we can recruit 4-5 patients per week, over 12 weeks.

Randomization Procedure: All participants will receive inpatient tobacco cessation counseling. We will randomize participants to one of two treatment arms: (1) ETC, where participants are referred at discharge to a quit line or outpatient smoking cessation group; or (2) PN: a patient navigator to coordinate tobacco treatment with the smoker's outpatient healthcare team and address any underlying social determinants of health that are barriers to cessation (identified using a validated social determinants of health screening tool).

Eligible patients who are interested in the study and provide informed consent will be randomized and informed of the randomization assignment by the research assistant. We will stratify randomization by participants' response regarding their plan to quit smoking ("I plan to stay quit" or "I plan to try to stay quit"). A computer-generated sequence of random numbers will assign treatment groups.

Data Collection: We will collect data by phone at 3 months post-randomization.

Retention: We expect to retain at least 60% of participants from baseline to 1-month follow-up, based on our prior experience conducting assessments at 3 (70% retention) and 6 months (76% retention) in similar populations. To maximize retention we will collect contact information including home address, phone, cell phone, beeper, e-mail, and phone numbers of three contacts. We will provide \$20 for completion of the 1-month assessment.

Patient Navigation Intervention: We base our intervention on the Social Contextual Model, a multi-level approach to health education which stresses the influence of life experiences (e.g. stress and financial problems) and social relationships (e.g. social networks and family roles) on the practice of health behaviors.

Participants will meet the navigator in person if she is available, or will be introduced by telephone. Participants will receive navigation from a trained navigator, based centrally in the Section of General Internal Medicine. The navigator has a BA degree, has extensive experience doing community health outreach, and has previously completed the University of Massachusetts "Basic Skills for Working with Smokers Online Course." Participants will receive up to ten hours of patient navigation, in person or over the phone, over a one-month period. We chose a two-hour intervention dose based on 1) a prior study of MI in low-income smokers and 2) our prior work studying navigation to promote smoking cessation. We have not designated a specific number of contacts, but allot a maximum of ten hours of patient navigation time per participant. The navigator will work flexible hours, contacting patients on evenings and weekends as necessary. Patient navigation contacts will involve individual counseling to help the patient achieve abstinence. We will adapt and incorporate into the PN script a modified version of the WE CARE Survey, which consists of 12 questions designed to: (1) identify six unmet material needs (inadequate education, employment, food security, housing, childcare, and household heat) by self-report (e.g., Are you employed?) and 2) determine whether participants would like assistance with each problem (e.g., If No, do you want help?). The survey takes less than five minutes to complete and has a test-retest reliability of 0.92.7 Thus, navigators will screen participants for social determinants of health which

may be preventing them from quitting smoking. Patient navigation intervention calls will use MI strategies to: (1) Assess stage of change for smoking cessation; (2) Assess/reinforce prior abstinence from smoking and/or efforts made to reduce/quit smoking; (3) Explore patient's motivation to quit, drawing on recent illness, financial situation, and family situation as appropriate; advise about the risks of smoking/benefits of quitting (4) Discuss past experience with utilizing cessation support; (5) Explore potential barriers to using smoking cessation medications (e.g. lack of trust, cost, misconceptions about treatment (e.g. that nicotine replacement therapy (NRT) is more harmful than cigarettes)); (6) Brainstorm strategies to address identified barriers; (7) Elicit commitment to accept another patient navigation counseling call, discuss timing.

Minimum navigation intervention dose: completion of MI calling script with the navigator

Navigator Training and Evaluation. We will train the navigator in issues of relevance to recently hospitalized patients (e.g. how to make follow-up appointments and assist with issues that arise with post-discharge medications). We will also train the navigator in tobacco treatment and barriers to treatment engagement among poor/minority patients (including how to screen for/address social determinants of health). The BNI-ART Institute at the BU School of Public Health will deliver a standard, validated MI booster training program. This training will occur over a half-day and focus on reviewing MI skills and delivery of the intervention. MI skills will be reviewed through didactics, demonstrations, roleplays, and video. The navigator will be evaluated on both process (helpfulness, warmth, empathy), and content (intervention adherence). Following training, [name] will meet weekly with the navigator to ensure skill maintenance by reviewing audiotapes of intervention calls and providing corrective feedback.

Preserving Internal Validity/Treatment Fidelity, and Program Tracking. The intervention is manual-based. After each patient interaction, the navigator will complete a checklist of intervention components that were delivered. We will use these checklists to ensure that the intervention is delivered as intended, and to estimate intervention "dose" and treatment exposure. We will audiotape 5 participant interactions with permission from the participant; [name] will monitor tapes for protocol adherence.

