## 8 Study Procedures

## 8.1 Screening and Recruitment

First, medical record (MR) will be accessed to determine (1) if patient is a current smoker (patients must be current smokers), (2) age of participant (must be age 18 or greater), (3) currently hospitalized on the general internal medicine or family medicine services or hospitalized within the past month, (4) have a primary care provider at BMC, (5) an estimated life expectancy of <12 months and (6) medical instability.

For patients that have not been excluded by MR review, the following questions will be asked to confirm eligibility:

How old are you? (must be  $\geq$  18)

Are you a current smoker? (smoked at least 1 cigarette per day in the past month)

Do you have a working telephone? (must have working telephone)

Do you read, understand or speak English? (must read, understand, and speak English)

Are you able and willing to provide informed consent? (must be willing and able to provide informed consent) When, if ever, do you plan to quit smoking cigarettes? (must have plans to quit smoking within 6 or more years)

The first contact could be made in-person prior to discharge, or over the phone, if patient has been discharged.

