#### 8.3 Randomization

Randomization will occur after RA obtains informed consent from the participant. Participants will be randomly allocated in a 1:1 ratio to the intervention or comparator arm.

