# 11.2 Sample Size Determination

The aim of this study is to determine the acceptability and feasibility of an adapted patient navigation smoking cessation intervention by pilot-testing it among 25 smokers at a large urban safety-net hospital. We will conduct a pilot RCT,

randomizing fifty hospitalized smokers to one of 2 study arms. We believe an n of 50 is the necessary sample size to determine acceptability and feasibility, and to have publishable results.

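### Randomisation is stratified by quit plan, but the analysis does not pre-specify that factor, and no restriction method within strata is stated

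*Combined protocol and SAP*

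**What the plan says.** **Allocation.** Section 4 (Randomization Procedure) states: "We will stratify randomization by participants' response regarding their plan to quit smoking". It names two answers, planning to stay quit and planning to try to stay quit. The sequence is described in one sentence: "A computer-generated sequence of random numbers will assign treatment groups". Section 8.3 adds the ratio: "Participants will be randomly allocated in a 1:1 ratio to the intervention or comparator arm". Neither section mentions blocks, block sizes, a separate list for each stratum or minimisation. In Section 4 the research assistant who screens and consents patients also assigns them and tells them the result.

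**Numbers.** Section 11.2 plans "randomizing fifty hospitalized smokers to one of 2 study arms" and describes the feasibility aim as "pilot-testing it among 25 smokers at a large urban safety-net hospital".

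**Analysis.** For 3-month cessation, Section 11.3 says "we will compare groups using chi- square tests", at the 0.05 level. It then plans a multiple logistic regression that takes in confounders found in bivariate analyses plus three variables fixed in advance: gender, age and race/ethnicity. Quit plan is not named. No between-arm test is named for the primary outcome, prescription sent.

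**Definition of the strata.** The inclusion paragraph of Section 4 reads "response is either: 'I plan to stay quit when I leave the hospital" and gives no second answer after the word 'either'. Section 6.1 asks only that the patient plan to quit. Section 8.1 screens with a different question: "When, if ever, do you plan to quit smoking cigarettes".

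**The concern.** A factor used to stratify randomisation should normally appear in the analysis. When allocation is balanced within strata, a test that ignores them uses a variance that still contains the between-stratum differences the design has removed, so it is too cautious. When allocation is not balanced within strata, adjustment is the only protection against a chance imbalance on the factor. Either way the stratum belongs in the pre-specified comparison. Section 11.3 leaves its inclusion to a screen run on the trial's own data.

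Separately, stratification balances a factor only if allocation is restricted within each stratum. Independent random numbers within strata give the same distribution of assignments as no stratification. The plan does not say which of these it will do.

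Quit intention could plausibly predict both cessation and medication uptake, though the plan itself does not say so. The pilot is meant to prepare a larger trial, so its between-arm estimates are likely to be carried forward.

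**Working it through.** **The plan's own figure.** 50 × 1/2 = 25, which matches the 25 smokers in the feasibility aim. No effect size, event rate or power lies behind the 50, so nothing else can be reproduced.

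**Inputs.** N = 50 (Section 11.2), ratio 1:1 (Section 8.3), two strata (Section 4), alpha 0.05 (Section 11.3). Stratum sizes, event rates and block size are assumptions, because the documents give none.

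**Step 1: blocks within strata, stratum ignored in the test.** Assume strata of 25 and 25, blocks of 4 and no treatment effect. With stratum rates a and b, the chi-square test works with pooled variance p(1 − p), where p = (a + b)/2. Under blocking the relevant variance is the average within strata, [a(1 − a) + b(1 − b)]/2.

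- 40% and 10%: pooled 0.25 × 0.75 = 0.1875; within (0.24 + 0.09)/2 = 0.165; ratio 0.165/0.1875 = 0.88. The effective critical value is 1.96/√0.88 = 2.09, a large-sample type I error of about 3.7%.
- 60% and 10%: pooled 0.35 × 0.65 = 0.2275; within (0.24 + 0.09)/2 = 0.165; ratio 0.725. The effective critical value is 1.96/√0.725 = 2.30, about 2.1%.

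Simulation at the actual sample size (10,000 runs per row) agrees in direction:

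| Assumed stratum rates | Unstratified chi-square | Cochran-Mantel-Haenszel |
|---|---|---|
| 20% / 20% | 5.8% | 5.1% |
| 30% / 10% | 4.9% | 5.0% |
| 40% / 10% | 4.0% | 4.6% |
| 60% / 10% | 2.6% | 5.0% |

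The stratified test stays near 5%, while the unstratified one falls as the factor becomes more prognostic. In one scenario with an effect (control rates 40% and 10%, plus 30 points in each stratum), power was 62.9% unstratified and 63.9% stratified.

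**Step 2: unrestricted sequence.** The size of one arm is then Binomial(50, 0.5).

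- Exactly 25:25: C(50, 25)/2^50 = 11.2%.
- 20:30 or worse: 2 × P(X ≤ 20) = 20.3%.
- The arms differ by at least 10 percentage points in quit-plan share with probability 48%, 44% or 38% for assumed strata of 25/25, 35/15 or 40/10. They differ by at least 20 points with probability 20%, 14% or 8%.

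The cost of an uneven split is small. Relative efficiency at 20:30 is 4 × 20 × 30/50² = 0.96. For an assumed 20% against 50%, power falls from 60.9% at 25:25 to 57.9% at 20:30.

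**Step 3: blocks of 4 within strata.** Over 5,000 simulated sequences for each of the same three stratum splits, the arms were never further apart than 26:24 and never differed by 10 points on quit plan.

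**Step 4: can the strata be formed?** The randomisation paragraph of Section 4 needs two answers, and its inclusion paragraph prints one. Read literally, everyone eligible falls in the same stratum. Section 8.1's question asks when the patient plans to quit, which does not sort patients into the two answers.

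**The case against.** A reader might infer that the trial uses a plain, unblocked sequence, so that neither the 1:1 ratio nor balance on quit plan is achieved. The documents do not support that. They are silent on blocking, and a computer-generated sequence can be blocked; stated stratification and a stated ratio fit a blocked list well. Even an unrestricted sequence is valid and 1:1 in expectation, and the 25 in the aim is a planning figure. The probabilities in Step 2 are therefore conditional on an unrestricted sequence.

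A reader might also infer that quit plan is never adjusted for. The logistic model could take it in through the bivariate screen, so the accurate criticism is that it is not pre-specified. Nor does the plan call quit plan prognostic; it gives no reason for stratifying on it. And the chi-square test is stated for a secondary outcome, so it cannot be described as the primary analysis.

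Finally, the harm is modest. Ignoring the stratum makes the test conservative when the factor is prognostic and allocation is blocked; it does not bias the comparison. An uneven split costs little power, and this is a feasibility pilot with no power calculation.

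All of this stands and limits the size of the point. It does not supply a reason to leave the stratification factor out of the pre-specified analysis.

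**Conclusion.** The point holds as a gap in specification. The factor used to stratify randomisation is missing from the pre-specified between-arm analysis, and a data-driven screen does not replace it. With blocks within strata, the loss is a test that runs at about 4.0% or 2.6% in place of 5% at assumed stratum rates of 40%/10% or 60%/10%. The power difference in the one scenario examined was one point. With little or no prognostic effect there is no such loss.

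The secondary point is that the restriction method is not stated. Only if the sequence is unrestricted does stratifying achieve nothing, with a 20% chance of 20:30 or worse and 96% relative efficiency at 20:30.

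The trial's validity is not in question. The change is worth making because it costs almost nothing, and because the strata cannot be applied as printed until the eligibility text is settled.

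**What to change.** 1. **Reconcile first.** Make Sections 4, 6.1 and 8.1 agree on which quit-plan question is asked, which answers make a patient eligible, and which answers define the two strata.
2. **Section 11.3.** Pre-specify the quit-plan stratum in the between-arm comparisons of prescription sent (primary) and 3-month cessation. Either a Mantel-Haenszel risk difference with a 95% confidence interval, or the stratum as a fixed covariate in the logistic model, would do. This also supplies the comparison now missing for the primary outcome.
3. **Section 4 or 8.3.** State permuted blocks of randomly varying size (for example 2 and 4) within each stratum, with upcoming assignments hidden from the enrolling research assistant. If blocking is already intended, this only records it.

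The cost is one or two sentences in each section and a setting in the randomisation program. No extra patients or data are needed, since the stratum is recorded at randomisation. The one drawback is that blocks make some assignments more predictable, which varying the block size and hiding the list both limit.
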